8.3.2 Secondary Effectiveness Analyses

The following analyses will be performed for secondary effectiveness variables:

- Within-treatment overall MFVDS responder rates at Month 1 (and 95% CI) for the cannula side and, separately, for the needle side will be displayed, with support from paired-comparison response categories [REDACTED]

[REDACTED]

- FACE-Q Satisfaction with Cheeks module (subject self-assessment) change from baseline at Month 1 Visit will be summarized with descriptive statistics.

[REDACTED]

Approval Date: 19-Oct-2017

[REDACTED]

8.3.4 Safety Analyses

ISRs, procedural pain assessment, and AEs will be summarized using descriptive statistics. The primary safety analysis of ISRs and AEs will be summarized by the percentage (and 95% CI) of subjects who have the ISR (or AE) on both sides, by the percentage (and 95% CI) of subjects who have the ISR (or AE) on the cannula side and not on the needle side, and by the percentage (and 95% CI) of subjects who have the ISR (or AE) on the needle side and not on the cannula side. Also, the within-treatment percentage (and 95% CI) of subjects who have the ISR (or AE) will be summarized for the cannula side and, separately, for the needle side.

ISRs reported by subjects will be summarized by symptom, maximum reported severity, maximum reported duration (ie, calendar days from first occurrence to last reported occurrence during the 30-day ISR period), and number of ISR days (ie, calendar days with non-zero severity, after accounting for days with missing reports during the ISR duration). Adverse events will be summarized by System Organ Class and Preferred Term, and will be tabulated by duration, severity, causality, action taken, relationship to treatment, and outcome. The summary will include incidence rate as well as total number of events. AEs that occur before treatment will be listed, but not summarized.

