4.5 Treatment Allocation Ratio and Stratification

Subjects will be randomized in a 1:1 ratio to receive treatment on the first side with the cannula or needle.

5. Study Population

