5.1 Number of Subjects

Up to 75 subjects will be enrolled at up to 7 sites in order to have 60 subjects treated.

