Typical or expected AEs or risks include bruising, swelling, redness, tenderness, and/or itching at the treatment site. Additional information about the possible side effects is available in the IDFU for VOLUMA XC.

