4.2 Study Objectives and Endpoints

The objective of this study is to evaluate the safety and effectiveness of VOLUMA XC injectable gel using cannula in subjects seeking correction of age-related volume deficit in the mid-face.

The study primary objective, secondary objective, and other objectives are presented with corresponding endpoint(s) below:

Table 4-1 Study Objectives and Corresponding Endpoints

Objectives	Endpoints	
To evaluate the safety and effectiveness of cannula versus needle for the correction of age-related volume deficit in the mid-face.	Primary Endpoint: • MFVDS response distribution by treatment, based on EI assessment on a 6-point scale of ordinal categories, from 0 to 5 (none, minimal, mild, moderate, significant, severe), for baseline and change from baseline to month 1 (primary endpoint)	
	 MFVDS responder rates by treatment, based on EI assessments on a 6-point scale of ordinal categories, from 0-5 (none, minimal, mild, moderate, significant, severe), with responders defined as ≥1 grade improvement from baseline, for month 1 (primary measurement time) Subject's FACE-Q Satisfaction with Cheeks, at the subject level rather than by treatment (because the questions are asked regarding the face rather than the treatment sides), for the 	

FACE-Q Rasch transformed score (0-100), which is converted from the sum score (range 5-20) across 5 items (symmetric, smooth, attractive, contour, and fullness), with each item scored on an ordinal scale from 1 to 4 (very dissatisfied, dissatisfied, satisfied, very satisfied); the FACE-Q Rasch score will be summarized for baseline and change from baseline to month 1 (primary measurement time)

[figure not shown]
Safety Assessments

- AEs, separately for AEs at cheeks, not at cheeks and combined
- Procedural Pain, based on subject assessment on an 11-point scale,
 response distribution by treatment, and paired treatment comparison

of each subject's difference score (-10 to +10)

• Injection Site Responses (ISR), based on subject's 30-day diary, overall and for each of 10 categories (redness, pain after injection, tenderness to touch, firmness, swelling, lumps/bumps, bruising, itching, discoloration and other), response distribution by treatment, separately for presence, severity (none, mild, moderate, severe), number of ISR days (none, 1-3, 4-7, 8-14 and 15 or more), and total duration (none, 1-3, 4-7, 8-14 and 15 or more days)

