5.1.4.3 Injection Site Responses

ISRs recorded in subject diaries after treatment will be summarized by pre-defined symptoms.

Table 5-21 ISR Analyses

Endpoint	Description	Timing	Methodology
ISR incidence	Incidence of occurrence. Response	30 days post	Categorical counts
	distribution for cannula, needle, cannula	treatment	
	only, needle only.		
ISR severity	Maximum reported severity. Response	30 days post	Categorical counts
	distribution for cannula, needle, cannula	treatment	
	only, needle only.		
Number of ISR days	Number of days with ISR reported during	30 days post	Categorical counts
	the 30-day diary period. Response	treatment	
	distribution for cannula, needle, cannula		
	only, needle only.		
ISR total duration	Total duration from first instance of the	30 days post	Categorical counts
	ISR to the last instance of the ISR within	treatment	
	the treatment period, where last instances		
	means no further report to the end of the		
	30-day diary period. Response distribution		
	for cannula, needle, cannula only, needle		
	only.		

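### The primary analysis of injection site responses uses presence or absence only, and the readable plan gives their severity and days no within-subject contrast with a confidence interval

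*Protocol*

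**What the plan says.** Protocol 8.3.4 sets the main analysis: "The primary safety analysis of ISRs and AEs will be summarized by the percentage (and 95% CI) of subjects" with the response on both sides, on the needle side only, and, for the cannula, "by the percentage (and 95% CI) of subjects who have the ISR (or AE) on the cannula side and not on the needle side". It adds each side's own incidence: "Also, the within-treatment percentage (and 95% CI) of subjects who have the ISR (or AE) will be summarized for the cannula side", and likewise for the needle side. The same section then says that ISRs are summarised by symptom, maximum severity, maximum duration and number of ISR days. All of this is descriptive, and no hypothesis test is stated for ISRs.

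SAP Table 4-1 lists ISR presence, severity, days and duration as distributions by treatment, overall and for each of 10 categories. Days and duration are grouped as none, 1–3, 4–7, 8–14 and 15 or more. In SAP Table 5-21 the severity row begins "Maximum reported severity. Response". Like the days and duration rows, it asks for distributions for cannula, needle, cannula only and needle only, with categorical counts as the method.

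For procedural pain, SAP Table 4-1 asks for more: "response distribution by treatment, and paired treatment comparison" of each subject's difference score, from -10 to +10.

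On frequency, Protocol section 11 gives words and no rate: "Typical or expected AEs or risks include bruising, swelling, redness, tenderness, and/or itching at the treatment site".

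**The concern.** Each subject is his or her own control, and SAP Table 4-1 states the objective as cannula versus needle for safety as well as effectiveness. If a response is common on both cheeks, the devices are likely to differ mainly in how severe it is and how long it lasts. A subject with severe swelling on one cheek and mild swelling on the other counts as affected on both sides, so the paired presence contrast records no difference.

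The by-side severity and days distributions do include that subject, but they do not link the two cheeks. At stake is a direct, precise estimate of the safety contrast that the paired design was built to give. The daily diary already holds the data for it.

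**Working it through.** **No planned figure to reproduce.** The readable text gives no expected ISR rate, detectable difference or power for ISRs. What follows measures information under stated assumptions.

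**Inputs from the documents.** n = 60 subjects, both cheeks treated (Protocol 5.1: "Up to 75 subjects will be enrolled at up to 7 sites in order to have 60 subjects treated"); severity in four ordered grades; two-sided 95% intervals.

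**Assumptions.** Needle-side incidence 60–95%. Affected needle sides split 45/40/15% into mild/moderate/severe. Latent normal severity with within-subject correlation ρ = 0.5 or 0.7. Cannula lower by 0.4 latent SD.

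**Step 1: one case by hand (90% incidence, ρ = 0.5).** The needle threshold is z(0.10) = -1.2816.
- Cannula incidence = Φ(1.2816 - 0.4) = Φ(0.8816) = 81.1%.
- Both sides = Φ₂(1.2816, 0.8816; 0.5) = 76.1%.
- Needle only = 90.0 - 76.1 = 13.9%; cannula only = 81.1 - 76.1 = 5.0%.
- One side only = 18.9%, or 0.189 × 60 = 11.3 subjects.

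**Step 2: all cases.** Cells give the values for ρ = 0.5 and ρ = 0.7, lower first. The last two columns give the chance that an exact two-sided 5% sign test (McNemar) on 60 subjects would detect the assumed shift. The first applies it to presence; the second applies it to each subject classed as cannula worse, same or needle worse on maximum severity.

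| Needle incidence | Both sides | Both, at different severity | One side only | Presence | Severity class |
|---|---|---|---|---|---|
| 60% | 34–38% | 20% | 28–35% | 47–58% | 59–78% |
| 80% | 59–62% | 30–32% | 23–29% | 39–47% | 66–84% |
| 90% | 76–78% | 35–39% | 16–19% | 25–30% | 66–84% |
| 95% | 86–87% | 37–43% | 10–12% | 13% | 64–81% |

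A second model (50/35/15% split, ρ = 0.5 or 0.8, paired t-test on the grade, 1,500 simulated trials per setting) agrees in direction. At 90% incidence it gives 24–34% for presence and 76–96% for severity; at 50%, 47–66% and 66–92%.

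**Step 3: why presence fades.** An exact two-sided test needs at least 6 discordant subjects, all in one direction: 2 × 0.5⁶ = 0.031, but 2 × 0.5⁵ = 0.063. With 95% incidence on both sides and independent cheeks, the expected number is 60 × 2 × 0.95 × 0.05 = 5.7. Positive correlation lowers it further.

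**Step 4: what the by-side tables give and withhold.** With both cheeks scored, the difference between the two marginal mean grades equals the mean paired difference, so the size of a severity shift can be recovered. Its precision cannot: Var(difference) = V(needle) + V(cannula) - 2Cov, and the covariance is not in either margin. At 80–95% incidence, the ratio of paired to unpaired standard error, √[1 - 2Cov/(V(needle) + V(cannula))], is 0.62–0.76. For days, even the mean difference is lost, because the categories are grouped and open-ended at 15.

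**Step 5: what a paired days estimate would give.** If the SD of the within-subject difference were 5 days (assumed), the 95% half-width would be 2.00 × 5/√60 = 1.3 days.

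**The case against.** The strongest reply is that little is hidden. The primary analysis also reports the both-sides percentage and each side's incidence, all with CIs, so concordant subjects are counted. Severity, days and duration are tabulated by side. In the 90% case, the planned tables would show moderate or severe responses on about 50% of needle sides and 34% of cannula sides, and incidence of 90% against 81%. No ISR test is planned, so detection rates are not a property of this plan. This stands.

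A reader might infer that most subjects add nothing, or that a real difference would be missed. The documents support neither. They give no ISR rate, and their list of expected reactions does not name firmness, lumps/bumps or discoloration, which are analysed separately. At 60% incidence, presence still carries much of the information.

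It can also be said that absence cannot be proved from this copy. The method definitions promised in SAP 5.1.1.3 are not readable. The pain comparison promised in Table 4-1 has no visible analysis in SAP 5.1.4, so the visible safety text is not the whole. The incidence row, for which the Protocol requires CIs, carries the same categorical-counts label. And *cannula only* is not defined for severity or days: applied grade by grade, it would capture part of the contrast.

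These points limit the claim but do not remove it. Where the SAP wants a paired contrast it says so: Table 4-1 for pain, and Tables 5-12, 5-15 and 5-16 for injection ease, MFVDS change and responders. The ISR entries in Tables 4-1 and 5-21 do not.

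**Conclusion.** The point holds in a limited form. The analysis labelled primary for ISRs is presence or absence, and no within-subject contrast with a CI for severity, days or duration appears in the readable text. A difference would be visible descriptively but not estimated with paired precision.

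The size depends on incidence, which is assumed here. At 80–95% on the needle side, 59–87% of subjects are affected on both sides and 30–43% of all subjects are affected on both at different severity. Presence would detect the assumed 0.4 SD shift in 13–47% of trials, against 64–84% for the paired severity classification. At 60% the figures are 47–58% and 59–78%. The problem is greatest for ISRs taken overall, whose incidence cannot be below that of the commonest symptom.

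The primary effectiveness conclusion is unaffected. The change is worth making because the safety comparison is a stated objective.

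**What to change.** In SAP Table 5-21 and Protocol 8.3.4, for each ISR and overall, among subjects with both cheeks treated:

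1. Give the percentage, with 95% CI, whose maximum severity was worse on the cannula side, the same, or worse on the needle side.
2. Give the within-subject cannula-minus-needle difference in number of ISR days, ungrouped, with its 95% CI.
3. Define *cannula only* and *needle only* for severity, days and duration: either the response is present on that side alone, or the category is reached on that side alone.

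Keep the existing tables and the descriptive status. If the unreadable SAP definitions already provide items 1 and 2, a cross-reference in Table 5-21 is enough.

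The cost is a few more descriptive table panels from diary data already collected, with no new visits or subjects. The wording should be settled before database lock.

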8.4 Subgroup Analyses

The primary effectiveness endpoint will be summarized by baseline overall MFVDS score and investigational site. Details will be provided in the statistical analysis plan.

[REDACTED]

Approval Date: 19-Oct-2017

[REDACTED]

[REDACTED]

8.6 Interim Analyses

No interim analysis is planned.

9. Materials

9.1 Study Treatment

[REDACTED]

9.1.2 Instructions for Use and Administration

For investigational use in this clinical study, VOLUMA XC dermal filler will be injected to the cheek area using the supplied [REDACTED] cannulas or needles [REDACTED] and aseptic injection technique. The TI will inject the treatment slowly using gentle, even pressure on the

Approval Date: 19-Oct-2017

syringe in accordance with the randomization scheme and the IDFU, which will be provided to the TI.

9.1.3 Treatment Regimen Adjustments

The TI will determine the appropriate volume of VOLUMA XC to inject based on his/her clinical experience, [REDACTED]

9.2 Other Study Supplies

The investigational site is responsible for urine pregnancy tests (sensitivity ≥ 50 mIU/mL for human chorionic gonadotropin), routine supplies related to device storage, administration, and follow-up visits (eg, antiseptics, drapes, gloves, gauze, anesthesia, ice packs, blood pressure cuff, and internet connection for eCRF completion and IWRS).

10. Study Administration Procedures

The clinical study shall not begin until the required approvals from the appropriate regulatory authorities and IRBs have been obtained.

10.1 Subject Entry Procedures

10.1.1 Overview of Entry Procedures

Prospective subjects as defined by the criteria in Sections 5.3 and 5.4 (inclusion/exclusion criteria) will be considered for entry into this study. A subject is considered to have entered the study upon signing the ICF, which will occur prior to any screening procedures.

Screening procedures include:

- [REDACTED]

Approval Date: 19-Oct-2017

10.1.2 Informed Consent and Subject Privacy

The purpose, procedures, risks, benefits, and alternatives to study participation will be discussed with each potential subject. The subject must also give Authorization for Use and Release of Health and Research Study Information, including digital images and other written documentation in accordance with the relevant country and local privacy requirements (where applicable) prior to any study-related procedures or change in treatment.

The TI or his/her authorized designee conducts the informed consent (IC) discussion and will document in the subject's medical records the acquisition of IC and the subject's agreement or refusal to notify his/her primary care physician about the study. The IC shall include all aspects of the study that are relevant to the subject's decision to participate throughout the study. The IC process is to avoid any coercion or undue influence on, or inducement of, the subject to participate. The subject is to personally sign and date the ICF. The TI or his/her authorized designee will retain the original copy of the signed form, and the subject will receive a copy. Upon signing the ICF, the subject is considered to be enrolled in the study and receives a subject number that will be used on all documentation for the subject throughout the study. Subject numbers will be assigned in ascending order, and numbers will not be omitted or reused. The subject number is coupled with the study number and site identification number for unique identification of each subject. The TI is to ensure important new information is provided to new or existing subjects throughout the study. Arrangements shall be made to inform the subject or legally authorized representative, as soon as possible, about the subject's inclusion in the study and about all aspects of the study. The subject shall be asked to provide IC for continued participation as soon as his/her medical condition allows.

10.1.3 Method for Assignment to Treatment Groups

All subjects will have 1 cheek treated with VOLUMA XC injectable gel using a [REDACTED] cannula and the contralateral cheek treated using a [REDACTED] needle. The side of treatment (ie, side of face for needle or cannula) will be randomized based on a central randomization schedule. An automated IWRS will be used to manage the randomization assignment based on a randomization scheme prepared by Allergan. Study treatments will be labeled with kit numbers. The IWRS will provide the site with the specific kit number(s) for each randomized subject at the time of randomization. Sites will dispense treatment according to the IWRS instructions provided by the system. Kit numbers used for actual injection should be recorded on eCRFs in order to determine "as-treated" versus "as-randomized" treatment association.

10.2 Compliance with Protocol

The TI is responsible for compliance with the protocol at the investigational site. A representative of Allergan will make frequent contact with the TI and his/her research staff and will conduct regular monitoring visits at the site to review subject and device accountability records for compliance with the protocol. Any protocol deviations will be discussed with the TI upon identification. The use of the data collected for the subject will be discussed to determine if the data is to be included in the analysis. All protocol deviations will be reported to the IRB according to the IRB's reporting requirements.

10.3 Pregnancy

If a female subject becomes pregnant after treatment, the TI will notify Allergan immediately after the pregnancy is confirmed. The TI will (1) instruct the subject to notify her physician of the presence of the investigational device and (2) will follow the pregnancy to term. Best practices are to be followed in order to ensure the welfare of the subject and the fetus. The Medical Safety Physician will contact the TI to obtain information about the pregnancy outcome. The subject will continue to be followed for safety, and the pregnancy will be documented as a protocol deviation.

Pregnancy by itself will not be considered an AE or serious adverse event (SAE). Hospitalization for a normal delivery or elective abortion of a normal fetus does not constitute an SAE. However, the occurrence of an adverse pregnancy outcome for the mother or child may constitute an AE or SAE, and these are to be reported as described in Section 11.3 and 11.4.

10.4 Study Termination

If conditions arise during the study that indicate that the study or an investigational site needs to be terminated, Allergan, the TI, monitor, IRB, and/or regulatory agencies will discuss the situation and take appropriate action after consultation. Conditions that may warrant termination of the study or site include, but are not limited to:

- the discovery of an unexpected, serious, or unacceptable risk to subjects enrolled in the study
- the decision on the part of Allergan to suspend or discontinue testing, evaluation, or development of the study device
- failure of the TI to comply with pertinent national or state regulations, IRB-imposed conditions, or protocol requirements

- TI submission of knowingly false information to Allergan, a study monitor, the IRB, or any regulatory agency

Per International Organization for Standardization (ISO) 14155, if a study is prematurely terminated or suspended due to safety issues, Allergan shall inform all Investigators and the regulatory authorities of the termination or suspension and the reason(s) for the termination or suspension. The IRB is also to be informed promptly and provided the reason(s) for the termination or suspension by Allergan or by the Investigator, as specified by the applicable regulatory requirements. If a premature termination or suspension occurs, Allergan shall remain responsible for providing resources to fulfill the protocol obligations and existing agreements for follow-up of subjects enrolled in the study, and each Investigator or authorized designee shall promptly inform enrolled subjects, if applicable.

11. Adverse Events

Throughout the course of the study, all AEs will be monitored and reported on an AE eCRF, including seriousness, severity, action taken and relationship to study treatment. If AEs occur, the first concern will be the safety of the study subjects.

Although the risk of developing a serious complication is small, the TI and the research staff will monitor each subject closely, and, if a complication occurs, they will use their medical judgment to do whatever is necessary to treat the problem. If subjects have any ongoing treatment-related AE at the time of the final visit, they must continue to be followed up until resolution of these events or the subject condition is considered stable by the TI. After the final visit, the subject will resume receiving the standard medical care according to the standard care of the clinic.

Typical or expected AEs or risks include bruising, swelling, redness, tenderness, and/or itching at the treatment site. Additional information about the possible side effects is available in the IDFU for VOLUMA XC.

11.1 Definitions

11.1.1 Adverse Event

An AE is defined in accordance with ISO 14155 as “any untoward medical occurrence, unintended disease or injury, or untoward clinical signs (including abnormal laboratory findings) in subjects, users, or other persons, whether or not related to the investigational medical device.” This definition includes events related to the investigational medical device or comparator and events related to the procedures involved except for events in users or other persons, which only include events related to investigational medical devices.

Disease signs and symptoms that existed prior to the study treatment are not considered AEs unless the condition recurs after the subject has recovered from the pre-existing condition or the condition worsens in intensity or frequency during the study.

AEs will be monitored throughout the study beginning with signing of the ICF. At each postscreening visit, the TI (or designee) will begin querying for AEs by asking each subject a general, non-directed questions, “Have you had any changes to your condition since your last visit?” Previous AEs and changes in therapy/concomitant medications are to be updated. Directed questioning and examination will then be done as appropriate. All reportable AEs and clinically significant abnormal laboratory findings will be documented on the appropriate eCRF.

The following is a list of known potential AEs:

- redness, swelling, or a rash, which may be associated with itching, pain on pressure, after the injection
- pain at injection site
- bruising
- nodules or “lumpiness” at the injection site
- discoloration of the injection site
- rare cases of allergy, severe sensitivity, localized inflammation and abscesses
- very occasionally, delayed side effects can occur many months after the treatment. These side effects may appear as red lumps showing up underneath the skin, or intermittent episodes of swelling.
- in rare circumstances, facial fillers have been injected into blood vessels causing blockage and embolization which can result in skin necrosis, ulceration, or vision changes. Risks to vision include complete blindness, partial blindness, blurred vision, double vision, loss of peripheral vision, loss of a portion of the visual field or anterior

segment ischemia (characterized by decreased vision and pain). These effects can be temporary or permanent but are rare.

- swelling or edema around the eye following an injection can result in a temporary decrease of vision.
- in rare circumstances, facial fillers have been associated with granulomas, which are small inflammatory nodules under the skin.

Unforeseeable risks or results are also a possibility. The risk of developing a serious complication is small. If a complication occurs, subjects will be advised to contact the TI who will use his/her medical judgment to do whatever is necessary to treat the subject.

